10.5.1 Analysis of Safety Data

All safety assessments will take place in the full analysis population. All subject-level percentages will be supplemented with two-sided 95% CIs computed via the Clopper-Pearson method. Summaries will include all events occurring on or after the date of first skin feed. Individual summaries (denominators for percentages) will be limited to the number of subjects within the appropriate analysis population with data available.

All unsolicited AEs, including serious and/or severe AEs will be coded according to the Medical Dictionary for Regulatory Activities (MedDRA) version 20.1 or later. A summary table will be prepared for unsolicited AEs presenting incidence of any AE, any related AE, any serious AE, any severe AE, any AE of grade ≥ 2 , any related AE of grade ≥ 2 , and any AE leading to study withdrawal where a subject only contributes once.

10.5.2 Analysis of Primary Objectives

Oocyst prevalence

The variation in the proportion of infected mosquitoes with at least one oocyst (oocyst prevalence) in DSFA and DMFA performed at two consecutive time points in the same human subject will be assessed with the per protocol population. Summary statistics will be provided for each assay and by time point (first and second). Additionally, Pearson correlation coefficients and estimates of total variation decomposed by between and within person variation will be summarized for both DSFA and DMFA. A paired t-tests will be used to evaluate the equivalence hypothesis for DSFA and DMFA. Mean differences and the corresponding 95% confidence intervals (CIs) will be provided.

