Out of the 60 mosquitoes in each cup, it is estimated that approximately 5% will not feed. Therefore 29 will be held up to Day 9 or Day 10 post feed for oocyst count determination and the remaining 28 will be held up to Day 14 or Day 15 post feed for sporozoite count determination. The maximum anticipated mortality for mosquitoes held to D9/D10 is approximately 15%, while for those held to D14/D15 is approximately 50%. Thus, at least 25 mosquitoes will be available for oocyst counts and at least 15 for sporozoite counts as described in section 8.1.9.3 below. This is summarized in the figure below.

Figure 8: Disposition of mosquitoes after the feeding assays

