[figure not shown]

With these limitations in mind a simulation approach was used to understand the power to reject various equivalence null hypotheses ($-\Delta_E, \Delta_E$) assuming either high correlation within subjects for consecutive DSFA or independence between measurements.

Briefly, we assume that the number of positive mosquitos for any DSFA is binomially distributed $x_{it} \sim \text{Bin}(25, p_{it})$ where $p_{it} \sim \text{Beta}(1.5, 6)$. The parameters for the Beta distribution were selected to generate a distribution of positive mosquitos which achieves, approximately, the characteristics listed in points 3 and 4 above (16% with 0 positive mosquitos and 50% less than 5). For a single draw of $x_t = x_{1t}, \dots, x_{36t}$, the distribution of mosquitos looks similar to the data observed above.

[figure not shown]
We considered two scenarios in our simulations. First, we assume that observations within person on consecutive days are independent. That is, $x_{i1} \sim \text{Bin}(25, p_{i1})$ and $x_{i2} \sim \text{Bin}(25, p_{i2})$ where p_{i1} and p_{i2} are independent draws from the Beta distribution. Second, we assume the underlying transmission probability within a person is constant for the two consecutive feeds and $x_{i1} \sim \text{Bin}(25, p_i)$ and $x_{i2} \sim \text{Bin}(25, p_i)$ where $p_i = p_{i1} = p_{i2}$. A simulated example for these two scenarios is shown in the figure below.

Figure 11. Simulating scenarios with independent daily transmission probabilities within subjects (left) or constant transmission probabilities over 24 hours within subjects (right).

[figure not shown]
We simulated this experiment based on both of the scenarios and then used a paired t-test to test for equivalence in oocyst prevalence at various equivalence intervals ($-\Delta_E, \Delta_E$). We find that with the current sample size of 36 subjects and 25 mosquitos per feeding assay, we will have 90% power to reject the null hypothesis that the difference of oocyst prevalence between consecutive feeding assays is greater than $+\/-7\%$ for correlated data (scenario 2). However, the same equivalence interval ($\Delta_E=0.07$) has only 4% power assuming independent data (scenario 1). Power for the equivalence test over a range of equivalence intervals and both scenarios are shown in the figure below.

Figure 12. Power calculation for equivalence test

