The data collected in this study will help inform the design of follow on studies by informing parameter values of interest, such as the correlation between subsequent feeds, to assess the power to measure monoclonal antibody or drug efficacy with before-after or two-group designs under various sample sizes and efficacy assumptions. For example, in the figures below independent data has an average correlation of 0.0 and is compared with a t-test and correlated data has an average correlation of 0.5 and is tested with a paired t-test. Using the parameters of the simulated data above we can investigate the impact of sample size and design on the power to detect varying levels of efficacy. The real data from this study will help inform this parameter space.

Figure 13. Estimated power calculation for follow-on Phase 2b trial design

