10.5.3 Analysis of Secondary Objectives

Oocyst density

The arithmetic mean oocyst density will be calculated for each subject by time point and assay. Distributions of subject-level means will be summarized by time point and assay. Medians will also be considered as a summary measure by subject. A generalized linear mixed model framework will be used

to incorporate the data from all mosquitos for each subject and summarize within and between person variability as well as summarize differences between time points. Variability and difference estimates (with 95% CIs) will be summarized for DSFA and DMFA. These analyses will be conducted on the per protocol population. A sensitivity analysis will be conducted using the full analysis population.

Sporozoite prevalence

The variation in the proportion of infected mosquitoes with at least one sporozoite in DSFA and DMFA performed at two consecutive time points in the same human subject will be assessed with the per protocol population. Summary statistics will be provided for each assay and by time point (first and second). Additionally, Pearson correlation coefficients and estimates of total variation decomposed by between and within person variation will be summarized for both DSFA and DMFA. A paired t-tests will be used to evaluate the equivalence for DSFA and DMFA. Mean differences and the corresponding 95% confidence intervals (CIs) will be provided.

Analysis of Exploratory Objectives

Oocyst and sporozoite density measured via qPCR

The arithmetic mean sporozoite and oocyst density as measured by qPCR will be calculated for each subject by time point and assay. Distributions of subject-level means will be summarized by time point and assay. Medians will also be considered as a summary measure by subject. A generalized linear mixed model framework will be used to incorporate the data from all mosquitos for each subject and summarize within and between person variability as well as summarize differences between time points. Variability and difference estimates (with 95% CIs) will be summarized for DSFA and DMFA. These analyses will be conducted on the per protocol population. A sensitivity analysis will be conducted using the full analysis population.

Assessing the relationship between oocyst and sporozoite density measured by DSFA and DMFA via microscopy and qPCR

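### Pearson r on per-cup prevalence includes mosquito-sampling error: under the protocol's own constant-infectivity scenario it is expected to reach only 0.77 for oocysts, so it should not be read as biological stability or carried unadjusted into the follow-on design

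*Protocol*

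**What the plan says.** Protocol section 5.2.1 defines oocyst prevalence as a proportion of the mosquitoes in a cup. For this endpoint section 10.5.2 plans summary statistics, a paired t-test for equivalence, and that "Pearson correlation coefficients and estimates of total variation decomposed by between and within person variation will be summarized for both DSFA and DMFA". Section 10.5.3 repeats this for sporozoite prevalence. For oocyst density, and later for the qPCR densities, section 10.5.3 says "A generalized linear mixed model framework will be used" on the data from all mosquitoes. No such model is named for prevalence.

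Section 10.3 gives the results a forward use: the study is to help design later trials by "informing parameter values of interest, such as the correlation between subsequent feeds". Its simulation draws the number of positive mosquitoes as Bin(25, p) with p from Beta(1.5, 6), "with the current sample size of 36 subjects and 25 mosquitos per feeding assay". In scenario 2, "we assume the underlying transmission probability within a person is constant for the two consecutive feeds".

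On mosquito numbers, section 8.1.5 states: "Thus, at least 25 mosquitoes will be available for oocyst counts and at least 15 for sporozoite counts". Section 10.5 leaves the full methods to an SAP.

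**The concern.** The study asks how much a person's infectiousness to mosquitoes changes over 24 hours. A proportion based on 25 mosquitoes, or on about 15, varies between two feeds even when the person has not changed at all. Pearson r between two such proportions mixes true day-to-day change with that sampling error, and so does any within-person variance computed directly on the proportions. The amount of error depends on how many mosquitoes were dissected and on the level of prevalence.

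Two things are at stake. First, an r well below 1 could be taken as evidence of biological instability when part or all of the shortfall is dissection noise. Second, section 10.3 would feed the correlation into power calculations for a trial that may use another mosquito number and in which an intervention is meant to lower p. Either change alters r with no change in the underlying biology.

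**Working it through.** **Inputs (Protocol 10.3 and 8.1.5).** p ~ Beta(1.5, 6), so a+b = 7.5; N = 36 subjects; m = 25 mosquitoes for oocysts. For sporozoites the stated minimum is 15, but "the remaining 28 will be held up to Day 14 or Day 15 post feed for sporozoite count determination" and about 50% mortality give 28 × 0.5 = 14.

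**The protocol's own figures first.** Simulating its model with a paired-t equivalence test at margin 0.07 and 0.025 per side (the level is not stated; 95% CIs are planned) gives:
- Scenario 1: 4.5% power, against the stated 4%.
- Scenario 2: 93-94% power, against the stated 90%. Power of 90% is reached at a margin of 0.066, so rounding of the margin probably explains the gap.

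The simulation model is therefore understood well enough to use.

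**Expected correlation with no true change.**
- Mean of p = 1.5/7.5 = 0.20.
- Var(p) = 1.5 × 6/(7.5² × 8.5) = 0.0188.
- E[p(1−p)] = 0.20 − (0.0188 + 0.04) = 0.1412.
- r = Var(p)/(Var(p) + E[p(1−p)]/m), which simplifies to m/(m + a + b).
- Within-person SD = √(0.1412/m).

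| Outcome | m | Expected r | Within-person SD (points) | Noise share of total variance |
|---|---|---|---|---|
| Oocysts | 25 | 25/32.5 = 0.769 | 7.5 | 23% |
| Sporozoites (same Beta assumed) | 15 | 15/22.5 = 0.667 | 9.7 | 33% |
| Sporozoites (same Beta assumed) | 14 | 14/21.5 = 0.651 | 10.0 | 35% |

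Simulated Pearson r for oocysts at N = 36 has mean 0.764 and a central 95% range of 0.58 to 0.89. True day-to-day variance is zero in every row.

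**Sensitivity to the Beta.** Beta(1.5, 6) gives 8.9% of feeds with no infected mosquito, against about 16% in section 10.3. Betas refitted to 16% zeros and 50-60% of feeds below 5 positives have these parameters and ceilings:
- 50% below 5: a+b = 0.711 + 2.187 = 2.90, so r = 25/27.90 = 0.90.
- 60% below 5: a+b = 0.967 + 4.437 = 5.40, so r = 25/30.40 = 0.82.

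For sporozoites the protocol gives no distribution. With a+b from 4 to 12 and m = 14-15, the ceiling runs from 14/26 = 0.54 to 15/19 = 0.79. The two refitted oocyst Betas would give 0.72-0.84.

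**Effect of an intervention.** Let day-2 p be k·p, with k = 1 − efficacy, no other change and m = 25. Then r = k·Var(p)/√(V₁V₂), where V₁ = 0.0188 + 0.1412/25 = 0.0245 and V₂ = k²·0.0188 + (0.20k − 0.0588k²)/25.

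| Efficacy | Expected r |
|---|---|
| 0% | 0.77 |
| 50% | 0.67 |
| 80% | 0.51 |
| 90% | 0.39 |

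Simulated means at N = 36 are about 0.01 lower.

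**Can the noise be removed?** Under scenario 2, subtracting p(1−p)/(m−1) from each day's variance gives a median corrected correlation of 1.02, with a central 95% range of 0.83 to 1.20 at N = 36. The attenuation is removed, at the price of an imprecise estimate.

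**The case against.** The strongest reply is that section 10.5.2 fixes less than it seems to. It names no scale, model or estimator for the variance split, section 10.5 calls these descriptions brief, and the SAP is not shown. That stands: the split may yet be done with a binomial mixed model, so the criticism of it is conditional. It does not rescue Pearson r, which is a named statistic on a per-cup proportion.

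Second, the numbers depend on the model. That also stands. The oocyst ceiling is milder under Betas that match the stated zero share, and the sporozoite figure borrows a distribution. The mosquito counts rest on maximum anticipated mortality, so they are minimums. With no mortality, 29 and 28 mosquitoes would both give about 0.79 under Beta(1.5, 6).

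Third, observed r is the right quantity for planning a paired t-test on proportions with the same mosquito number. This holds without an intervention effect; the efficacy table shows that it fails once p is lowered.

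A reader might also draw stronger conclusions that the protocol does not support:
- *That a sound before-after design would be rejected.* No decision rule on r or on within-person SD appears. The hypothesis in section 10.2 concerns the mean difference, which this noise does not bias, and section 10.3 illustrates correlated data with r = 0.5, well below the ceiling.
- *That DSFA and DMFA cannot be compared.* Planned totals are equal at 60 mosquitoes per subject and feed (one cup of 60; two cups of 30), so with the DMFA cups pooled any imbalance is speculative.
- *That the information is lost.* Oocysts are recorded for each midgut (section 8.1.9.3), so the separation can still be made.

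Finally, the check above used a moment correction, not the mixed model proposed below. With 36 subjects, two days and many low feeds, the day-to-day component will be estimated imprecisely.

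**Conclusion.** The point holds, as an inexpensive improvement and not as an error that invalidates the analysis. Under the protocol's own scenario 2, a population with no day-to-day change is expected to show an oocyst r of 0.77 and a within-person SD of 7.5 points that is entirely sampling noise. The ceiling is about 0.82-0.90 if the Beta is matched to the stated zero share. For sporozoites it is about 0.65-0.67 if the oocyst Beta applies, and roughly 0.54-0.79 for a+b between 4 and 12.

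These figures assume binomial sampling within a feed and a Beta distribution between people. The conclusion is firm for Pearson r and depends on the unstated scale for the variance split. Raw r remains usable for a comparison without intervention at the same mosquito number. It should not be taken as a measure of biological stability, nor transferred to other mosquito numbers or to a trial in which an intervention lowers p.

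**What to change.** In section 10.5.2, and for sporozoite prevalence in section 10.5.3, extend the mixed model already planned for densities to the infected yes/no result of each mosquito. Fit it separately for DSFA and DMFA, with a binomial outcome, a fixed day effect, and random subject and subject-by-day effects. Report the between-person and the day-to-day variance with 95% CIs, and the observed correlation that these imply at the planned mosquito number. Use the variance components, not raw r, as inputs to the follow-on power calculations.

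Keep Pearson r and the paired equivalence test, and label r as specific to the number of mosquitoes dissected. State that the variance split is made after removing mosquito-sampling error.

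The cost is a few sentences of protocol or SAP text and one more model per assay and outcome, on data already being collected. The downside is slightly more modelling, and wide intervals for the day-to-day component with 36-45 subjects.

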10.5.3 Analysis of Secondary Objectives

Oocyst density

The arithmetic mean oocyst density will be calculated for each subject by time point and assay. Distributions of subject-level means will be summarized by time point and assay. Medians will also be considered as a summary measure by subject. A generalized linear mixed model framework will be used

to incorporate the data from all mosquitos for each subject and summarize within and between person variability as well as summarize differences between time points. Variability and difference estimates (with 95% CIs) will be summarized for DSFA and DMFA. These analyses will be conducted on the per protocol population. A sensitivity analysis will be conducted using the full analysis population.

Sporozoite prevalence

The variation in the proportion of infected mosquitoes with at least one sporozoite in DSFA and DMFA performed at two consecutive time points in the same human subject will be assessed with the per protocol population. Summary statistics will be provided for each assay and by time point (first and second). Additionally, Pearson correlation coefficients and estimates of total variation decomposed by between and within person variation will be summarized for both DSFA and DMFA. A paired t-tests will be used to evaluate the equivalence for DSFA and DMFA. Mean differences and the corresponding 95% confidence intervals (CIs) will be provided.

Analysis of Exploratory Objectives

Oocyst and sporozoite density measured via qPCR

The arithmetic mean sporozoite and oocyst density as measured by qPCR will be calculated for each subject by time point and assay. Distributions of subject-level means will be summarized by time point and assay. Medians will also be considered as a summary measure by subject. A generalized linear mixed model framework will be used to incorporate the data from all mosquitos for each subject and summarize within and between person variability as well as summarize differences between time points. Variability and difference estimates (with 95% CIs) will be summarized for DSFA and DMFA. These analyses will be conducted on the per protocol population. A sensitivity analysis will be conducted using the full analysis population.

Assessing the relationship between oocyst and sporozoite density measured by DSFA and DMFA via microscopy and qPCR

Pearson correlation coefficients and Bland-Altman plots will be used to explore relationship between density measures as measured by DSFA and DMFA via microscopy and qPCR. The regression framework described above will be expanded to explore mean differences in measures. Estimated mean differences and corresponding 95% CIs will be reported. These analyses will be conducted on the per protocol population. A sensitivity analysis will be conducted using the full analysis population.

10.6 Handling of Dropouts and Missing Data

In this experimental medicine study, missing data will be assumed to be missing completely at random, and only observed data collected from participants and available in the appropriate study population will be used for analysis.

10.7 Timing of Analyses

Upon completion of the second DSFA and DMFA for the final participant, a topline analysis will be initiated to include the results of the primary and secondary oocyte prevalence and density results.

Following collection of the remainder of the data and database lock, all results will be described in a peer reviewed publication.

11. SOURCE DOCUMENTS AND ACCESS TO SOURCE DATA/DOCUMENTS

The KCRC site will maintain appropriate medical and research records for this trial. Source data are all information, original records of clinical findings, observations, or other activities in a clinical trial necessary for the reconstruction and evaluation of the trial.

12. QUALITY ASSURANCE AND QUALITY CONTROL

The KCRC site has SOPs for quality management that include staff training methods, product accountability records, specimen tracking logs, questionnaires, audio or video recordings.

13. ETHICS/PROTECTION OF HUMAN SUBJECTS

13.1 Ethical Standard

This study will be conducted in accordance with the latest revision of the Declaration of Helsinki (2013), the Medical research Involving Human Subjects act (WMO), the ICH Good Clinical Practice, Department of Defense (DoD) requirements as outlined in 32 CFR 219, 45 CFR 46 and local rules of KEMRI SERU. The investigators are responsible for obtaining all relevant ethical approvals of the protocol and any subsequent amendments in compliance with local law before the start of the study.

13.2 Institutional Review Board

13.2.1 Ethics Approval

Submission of the protocol and supporting documents will occur in accordance with local regulatory requirements. KEMRI SERU is the IRB of record for the Kenyan Site, Kombewa in Kisumu. This protocol will be submitted to KEMRI Center Scientific Committee for review and approval. It will also be submitted to the KEMRI SERU where ethical aspects of the protocol will be reviewed before the protocol can be approved.

The Walter Reed Army Institute of Research IRB will also be involved in the approval process for this protocol. WRAIR IRB is the IRB of record for US Army Medical Research Directorate-Africa (USAMRD-A). For this reason, approval from the WRAIR IRB will be sought alongside the KEMRI SERU approval prior to implementation of the protocol or protocol amendments for this study.

PATH will delegate ethical review and oversight to KEMRI SERU.

13.2.2 Protocol Amendments

All amendments and modifications will be submitted to the WRAIR IRB and KEMRI SERU for review and approval. No changes in protocol conduct will be implemented until approval is obtained from the

WRAIR IRB and KEMRI SERU, as applicable, unless required to eliminate apparent immediate hazards to the study subjects. Amendments and modifications cannot be implemented until the WRAIR Commander's Memorandum has been issued. The WRAIR HSPB will submit amendments to USAMRMC ORP HRPO as per WRAIR SOP UWZ-C-636.

Non-significant amendments from the sponsor that are defined as amendments that do not affect the safety and wellbeing of the subjects at the site, and that are more administrative will also require both WRAIR IRB and KEMRI SERU approval prior to implementation.

13.3 Informed Consent Process

13.3.1 Consent and Other Informational Documents Provided to Participants

Consent forms describing in detail the study procedures, and risks and benefits are given to the participant and written documentation of informed consent is required prior to starting the intervention.

13.3.2 Consent Procedures and Documentation

Discussion of risks and possible benefits of participation will be provided to the participants and their families. Consent forms will be IRB-approved and the participant (or the consent witness) will be asked to read and review the document. The investigator or designee will explain the research study to the participant and answer any questions that may arise. All participants will receive a verbal explanation in terms suited to their comprehension of the purposes, procedures, and potential risks of the study and of their rights as research participants. Participants will have the opportunity to carefully review the written consent form and ask questions prior to signing. Thereafter, signature of the written informed consent will be obtained from each participant who wants to participate in the study. The participant and the study staff conducting informed consent explanation will sign and date the consent form. The participant signature confirms that (s)he has understood the information. For illiterate individuals, the informed consent process will be conducted in the presence of a literate impartial witness selected by the participant but not a member of the CRC staff. The participant will thumb print the consent form and the witness will write the participant's name and sign and date the consent form. In case of any amendments to the protocol resulting in changes in study procedures, the participant will be informed, and additional informed consent will be obtained if necessary. In accordance with Good Clinical Practice, the volunteer may terminate participation in the study at any time for any reason without penalty. Additionally, if the participant is unable or unwilling to adhere to the protocol design, the investigator may terminate volunteer's participation. The study team will use the participant's preferred language usually English, Kiswahili or Luo, for informed consent. The participant will sign the informed consent document prior to any procedures being done specifically for the study. A copy of the informed consent document will be given to the participants for their records.

